### 6.3 SBRT dose specifications

- 6.3.1 The prescribed dose will be 40 Gy to the PTV, delivered at 8.0 Gy per fraction for a total of 5 fractions.
- 6.3.2 At least 95% of the PTV should receive 100% of the prescribed dose.
  - 6.3.2.1 Coverage of 90-95% of the PTV by 100% of the prescribed dose will be considered a minor but acceptable deviation whereas coverage of <90% by 100% of the prescription dose will be considered a major unacceptable deviation.
- 6.3.3 Rapid dose falloff outside the PTV is to be prioritized over PTV dose uniformity and may result in considerable dose heterogeneity within the PTV, but the maximum dose within the PTV should be limited to 130% of the prescription.

### 6.4 Critical Structures

The organ at risk planning guidelines for the study are given below. All reasonable attempts should be maintained to minimize radiation to organs at risk if PTV coverage is not compromised.

Pilot cohort (40 Gy in 5 fractions)*		
Organ	Volume	Dose (Gy)
Rectum	Maximum point dose (1cc)	≤ 38.06 Gy
	Less than 3cc	< 34.4 Gy
	90% of the rectum	≤ 32.625 Gy
	80% of the rectum	≤ 29 Gy
	50% of the rectum	≤ 18.125 Gy
Bladder	Maximum point dose (1cc)	≤ 38.06 Gy
	90% of the bladder	≤ 32.625 Gy
	50% of the bladder	≤ 18.125 Gy
Urethra	Maximum point dose	≤ 38.78 Gy
Femoral heads	Less than 10cc cumulative (both sides)	20 Gy

	Maximum point dose	30 Gy
--	--------------------	-------

\*Constraints used in prior UAB protocol of prostate SBRT that included 40 Gy in 5 fraction focal boost (NCT01856855).

## **6.5 Treatment plan physics quality assurance**

[figure not shown]
- 6.5.1 All treatment plan dose distributions will be verified by UAB staff physicists and must meet the quality assurance standards set forth by the Department of Radiation Oncology prior to patient SBRT administration.
- 6.5.2 Dose will be validated by either an ion chamber/film combination in a solid water phantom or a dose calibrated diode array. In either case, the phantom will be irradiated with the same plan as the patient including all couch angles and beam projections. A dose plane will be calculated and exported from the treatment planning system and will be compared with the measured dose plane from the one of the above techniques. Dose comparisons will be analyzed using the gamma criteria of 3%/3mm and will be considered valid if 95% of points have gamma values of less than 1.

## **6.6 Technical factors**

- 6.6.1 All treatment plans will be devised utilizing a volumetric modulated arc therapy (VMAT) approach. No restrictions are placed on the number and position of treatment arcs.
- 6.6.2 Treatments will be delivered on appropriately selected linear accelerators at the discretion of the treating physician

## **6.7 Treatment delivery**

- 6.6.1 Patients will be instructed to arrive in the clinic at least 1 hour prior to planned treatment delivery and a 16-french Foley catheter will be placed and urine allowed to drain. A Henschke style catheter containing 3 Calypso radiotransponder beacons will be placed into the urinary lumen of the Foley catheter as shown below:

- 6.6.2 Patients will be instructed to have an empty rectum for treatments. Utilization of bowel preparation with oral or suppository medications is left up to the treating physician. Endorectal balloons are not allowed on this study.
- 6.6.3 Image-guidance with kilovoltage orthogonal x-rays and cone beam CT scans are to be utilized prior to administration of each radiotherapy fraction. A physician is to approve appropriate patient positioning based upon set-up imaging, with the patient being aligned to the urinary catheter and prostate-rectum interface.
- 6.6.4 The positions of the transponders of the KV orthogonal x-rays and the CBCT will be compared with the dummy seed reference contours. The catheter position will be adjusted as needed. After

the patient is correctly positioned, the Calypso reference position (zero) will be set.

## **6.8 Treatment delivery schedule**

Radiation treatments will be delivered per the standard outpatient setting radiation oncology clinic. Treatment must be completed in within 17 calendar days, with day of first treatment being considered day 1. Exact treatment schedule is left to the discretion of the treating physician.

# **7.0 THERAPY MODIFICATIONS**

## **7.1 Non-Study Treatment**

- 7.1.1 All medications and other treatment taken by the subject during the study, including those treatments initiated prior to study enrollment, must be recorded within the medical record
- 7.1.2 Hormonal blockade agents such as leuprolide or bicalutamide will not be allowed in this study.
- 7.1.3 The use of standard prescription or non-prescription medication to manage symptoms of disease or treatment is left to the discretion of the treating physician. Examples of common medications prescribed for treatment of disease or radiation-related side effects will likely include tamsulosin, phenazopyridine, and/or loperamide

## **7.2 Concomitant Medication**

- 7.2.1 All medications administered since protocol enrollment will be recorded in the medical record
- 7.2.2 No cytotoxic chemotherapies or hormonal therapies are to be administered during the study evaluation period
- 7.2.3 Immediate pre or post-treatment usage of steroids (for example, dexamethasone 4 mg po one hour prior to radiation) is at the discretion of the treating physician.
- 7.2.4 Prophylactic (or continued) usage of tamsulosin or alfuzosin (or other alpha-blocker medication) allowed at the discretion of the treating physician.

## **7.3 Adverse Events (AE's) and Serious Adverse Events (SAE's)**

- 7.3.1 Definition of AE: Any untoward medical occurrence, which does not necessarily have a causal relationship with the study

Protocol Version: May 12, 2020

Amendment # 1

Page 15 of 26

treatment. This includes any physical or clinical change experienced by the subject, whether or not considered related to the study treatment. An AE can therefore be any unfavorable or unintended sign (including an abnormal lab finding, for example), symptom, or disease (including the onset of new illness and the exacerbation of pre-existing conditions) temporally associated with the study treatment. Progressive prostate cancer disease is not considered to be an AE. Typical symptoms of radiotherapy treatment including grade  $\leq 3$  urinary or gastrointestinal toxicity will not be considered an AE, though they will be documented in the medical record (section 9.0). AE's will be recorded in the medical record.

**7.3.2 Definition of SAE:** Any event occurring during the study evaluation period that results in any of the following outcomes

- Death
- Inpatient hospitalization
- Bleeding requiring administration of blood products
- Any grade  $\geq 3$  urinary or gastrointestinal toxicity

Note that urinary retention requiring temporary urinary catheter placement is considered a grade 2 toxicity by the CTCAE 4.03

All SAE's must be recorded in the medical record. The onset and end dates, severity, duration, effect on study administration (discontinuation/cancellation, for example), relationship to study treatment, and administration of any drugs or therapies to treat the SAE's will be recorded in the medical record.

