### **2.4 SBRT for prostate cancer**

The rationale for prostate SBRT stems from a combination of the theorized sensitivity of prostate cancer to larger fractions of radiation (i.e. low  $\alpha/\beta$ ) in combination with the ability of modern radiation planning, targeting, and delivery techniques to accurately administer higher doses of radiation with small uncertainty margins. A growing body of literature supports that prostate SBRT, typically with a dose of 36.25 Gy to the entire prostate over 5 fractions, is associated with toxicity rates similar to fractionated regimens. Early efficacy results also support that whole prostate SBRT is associated with high rates of biochemical control for men with NCCN defined low or low-intermediate risk prostate cancer. Recently, prostate SBRT was endorsed by the American Society for Therapeutic Radiation Oncology as an option for first-line therapy for men with low-risk prostate cancer.

At the University of Alabama at Birmingham prostate SBRT, has generally been performed as part of a recently completed prospective clinical trial (NCT01856855). In this study, the entire prostate gland was treated to a dose of 36.25 Gy in 5 fractions and MRI-defined focal nodules received a simultaneous integrated boost to 40 Gy in 5 fractions. This study met its primary safety endpoint of fewer than 15% of patients experiencing acute urinary retention requiring temporary placement of a Foley catheter (7.7% observed rate). Biochemical follow-up data are maturing.

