#### **7.4 Guidelines for adverse event recording**

**7.4.1** The Common Terminology Criteria for Adverse Events version 4.0 (CTCAE v4.0, [http://evs.nci.nih.gov/ftp1/CTCAE/CTCAE\\_4.03\\_2010-06-14\\_QuickReference\\_5x7.pdf](http://evs.nci.nih.gov/ftp1/CTCAE/CTCAE_4.03_2010-06-14_QuickReference_5x7.pdf)) will be used for grading adverse events

**7.4.2** The investigator must assess the relationship of any AE or SAE to the use of study treatment using the following guidelines outlined in the table below:

Table 7.5.3 ATTRIBUTION OF ADVERSE EVENTS		
Code	Descriptor	Definition
5	Definite	The adverse event is clearly related to the investigational treatment
4	Probable	The adverse event is likely related to the investigational treatment
3	Possible	The adverse event may be related to the investigational treatment

2	Unlikely	The adverse event is doubtfully related to the investigational treatment
1	Unrelated	The adverse event clearly not related to the investigational treatment

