## 8.0 STUDY PARAMETERS

- 8.1** For the purposes of this study, acute toxicity will be defined as event(s) that occur within 90 days of the completion of radiotherapy. Acute toxicity will be determined by both intra-treatment examinations and by scheduled follow-up evaluations after the treatment has completed. Late toxicity will be defined as any toxicity occurring > 90 days after the completion of treatment.
- 8.2** Baseline evaluations of enrolled patients must occur within six weeks of study enrollment
- 8.3** "Day 1" will be defined as the date of the first radiotherapy treatment. "Day 42/Week 5/Month 1" will represent the one month follow-up visit after the completion of the last radiotherapy treatment. Day 1 and Day 43/Week 5/Month 1 evaluations may be done within +/- 7 days of the specified day.
- 8.4** "Month 1, 3, 6, 9, 12, 18, and 24" will be defined as the respective follow up visits after the completion of radiotherapy. Month 3-24 evaluations may be done within +/- 30 days of the specified day.

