### **11.3 Toxicity evaluation**

- 11.3.1 Acute and late toxicity will be graded per the Common Terminology Criteria for Adverse Events version 4.0 (CTCAE v4.0,

[http://evs.nci.nih.gov/ftp1/CTCAE/CTCAE\\_4.03\\_2010-06-14\\_QuickReference\\_5x7.pdf](http://evs.nci.nih.gov/ftp1/CTCAE/CTCAE_4.03_2010-06-14_QuickReference_5x7.pdf).

- 11.3.2 Definition of acute toxicity: any possible, probable, or definite treatment-related AE or SAE occurring within three months of the completion of radiotherapy.
- 11.3.3 Definition of late toxicity: any possible, probable, or definite treatment-related AE or SAE occurring after three months of the completion of radiotherapy.

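### Toxicity in Section 11.3 must be an AE or SAE, but Section 7.3.1 strips AE status from typical urinary and GI toxicity, so non-serious grade 1–2 events drop out of the toxicity rate

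*Combined protocol and SAP*

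**What the plan says.** Early and late toxicity are secondary endpoints (Section 11.2.1). Section 11.5.1 has toxicity rates reported as proportions with exact binomial 95% confidence intervals.

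The statistical section defines acute toxicity as "any possible, probable, or definite treatment-related AE or SAE occurring within three months of the completion of radiotherapy" (11.3.2) and late toxicity as "any possible, probable, or definite treatment-related AE or SAE occurring after three months of the completion of radiotherapy" (11.3.3). Both definitions depend on what Section 7.3 calls an AE or an SAE:

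- Section 7.3.1, which defines an AE, takes out the typical symptoms of radiotherapy, including those of grade 3 or lower: "urinary or gastrointestinal toxicity will not be considered an AE, though they will be documented in the medical record".
- Section 7.3.2 limits SAEs to death, inpatient hospitalization, bleeding that needs blood products, and urinary or GI toxicity of grade 3 or higher. It adds that "urinary retention requiring temporary urinary catheter placement is considered a grade 2 toxicity by the CTCAE 4.03".

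Section 8.1 gives a second definition with no AE, SAE or relatedness condition: "acute toxicity will be defined as event(s) that occur within 90 days of the completion of radiotherapy", and "Late toxicity will be defined as any toxicity occurring > 90 days after the completion of treatment".

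On attribution, Section 7.4.2 says: "The investigator must assess the relationship of any AE or SAE to the use of study treatment". CTCAE grades are collected for any toxicity at the end of treatment and at each follow-up visit (Table 8.1, Sections 9.4.2 and 9.5.2). Section 11.5.2 lists toxicity results as a categorical variable without saying which definition applies.

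**The concern.** The events that lose AE status are the ones the trial most needs to describe. For whole-gland SBRT, Section 2.5 puts severe grade 3 toxicity at about 1% and the common grade 2 late complications at 5–15% each. It argues that a smaller irradiated volume may reduce such toxicity. Section 2.4 reports that the predecessor trial's primary safety endpoint was acute retention needing a temporary catheter, which Section 7.3.2 here classes as grade 2. A rule that keeps the rare grade 3 events and drops the common grade 1–2 events would make focal SBRT look safer than the recorded data show.

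With two definitions in force, the same 10 patients can also give two different rates, and the choice would fall to the analyst after the data are known.

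**Working it through.** **Step 1. Apply the definitions by grade.** Take a typical urinary or GI radiotherapy toxicity judged related to treatment.

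| Event | AE under 7.3.1? | SAE under 7.3.2? | Counted by 11.3? | Counted by 8.1? |
|---|---|---|---|---|
| Grade 1–2, no other SAE outcome | No | No | **No** | Yes |
| Retention with temporary catheter (grade 2 per 7.3.2), no other SAE outcome | No | No | **No** | Yes |
| Grade 1–2 with hospitalization or transfused bleeding | No | Yes | Yes | Yes |
| Grade 3 | No | Yes | Yes | Yes |
| Grade 4–5 | Not exempted | Yes | Yes | Yes |

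The first two rows are the gap. Grade 3 is counted, but only because Section 7.3.2 makes it an SAE after Section 7.3.1 has said it is not an AE.

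**Step 2. Check relatedness.** Section 11.3 needs a relatedness judgement, and Section 7.4.2 requires one only for AEs and SAEs. An exempted event will have a CTCAE grade but may have no relatedness code. An analyst who wanted to include it might then be unable to apply the Section 11.3 test.

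**Step 3. Reproduce the plan's own intervals.** Clopper-Pearson limits for x of n are the 2.5% quantile of Beta(x, n−x+1) and the 97.5% quantile of Beta(x+1, n−x). For 9/10 this gives (0.5550, 0.9975), width 0.4425. For 10/10 the lower limit is 0.6915. All agree with Section 11.6.1, so the same method is used below.

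**Step 4. Size of the discrepancy.** The documents give no toxicity rates for focal SBRT, so the counts are assumed. Suppose k of 10 patients have non-serious grade 2 urinary or GI toxicity and no patient has any other countable event.

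- Section 11.3 reports 0/10 whatever k is. The upper limit is 1 − 0.025^(1/10) = 1 − 0.6915 = 0.3085.
- Section 8.1 with k = 1 reports 1/10, CI (0.0025, 0.4450).
- Section 8.1 with k = 2 reports 2/10, CI (0.0252, 0.5561).

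**Step 5. Chance that the conflict matters.** The probability of at least one such event in 10 patients is 1 − (1 − p)^10.

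- Catheter retention at the predecessor's 7.7% (Section 2.4): 1 − 0.923^10 = 0.551. At an assumed 5% it is 0.401, and at an assumed 10% it is 0.651.
- A single grade 2 late complication at the 5–15% in Section 2.5: 1 − 0.95^10 = 0.401, up to 1 − 0.85^10 = 0.803.

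These rates come from whole-gland treatment (with a focal boost in the predecessor trial) and are used only for scale.

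**The case against.** The best defence is that Section 7.3.1 was meant only to keep expected symptoms out of AE handling, and that toxicity is a separate stream. The exempting sentence points to Section 9.0. Section 9.5.1 gives monitoring of acute and late toxicity as a purpose of follow-up, and Section 9.5.2 has any toxicity graded. Section 11.3.1 applies CTCAE without a grade floor, and Section 11.5.1 speaks of toxicity rates and not AE rates. On this reading, the AE-or-SAE wording in 11.3 is loose drafting. Calling a symptom typical of radiotherapy also half-implies that it is related.

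Much of this stands. The data are captured, the intent may well be as described, and nothing shows that the investigators plan to discard low-grade events. The probabilities in Step 5 are chances that an event occurs, not that it is left out of the report. The 0/10 and 2/10 intervals overlap heavily, and no toxicity threshold or stopping rule depends on the rate. The difference between 90 days and three months could move only an event at the boundary, and the grade 3 inconsistency does not alter the count.

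It does not remove the conflict. Section 7.3.1 is written as a definition and is not confined to reporting. Section 11.3.1 names only the grading scale, and the two items after it restrict toxicity to AEs and SAEs. Nothing in Sections 8, 9 or 11 says that this restriction yields to the broader wording. Recording an event does not decide whether the endpoint counts it.

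**Conclusion.** The concern holds. As written, the Section 11.3 definitions leave out typical non-serious grade 1–2 urinary and GI toxicity, and Section 8.1 counts it. The direction is clear: following Section 11.3 literally can only lower the reported rate relative to counting all related toxicity. The size depends on how many patients have such events and no other countable one; each adds 10 percentage points to the difference (1 of 10). At the whole-gland rates in the protocol, the chance that at least one of 10 patients has a given such event is roughly 40% to 80%.

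The harm is limited to a descriptive secondary endpoint. The primary feasibility endpoint, the 9-of-10 success rule and the sample size of 10 do not change. It should be fixed, because the stated rule would misreport the safety outcome on which the rationale for focal treatment rests.

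**What to change.** 1. In 11.3.2 and 11.3.3, define acute and late toxicity as any CTCAE v4.0 event, of any grade, judged possibly, probably or definitely related to treatment, whatever its AE status under 7.3.1.
2. Extend the attribution requirement in 7.4.2 to every graded toxicity, so that the relatedness condition can be applied.
3. Reconcile 8.1 (90 days, no attribution) with 11.3 (three months, attribution), so that one definition and one cut-off remain.
4. Reconcile 7.3.1 with 7.3.2 on the status of grade 3 urinary and GI toxicity.
5. Optionally, report the worst grade per patient for urinary and GI toxicity separately, in the acute and late periods. This would make the result easier to read, but the contradiction does not require it.

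The cost is wording changes in 7.3.1, 7.4.2, 8.1 and 11.3. No new assessments are needed. Attribution would have to be coded for all graded toxicity in 10 patients, retrospectively for any event already recorded without it. The reported toxicity rate may be less favourable than under the current wording.

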### **2.5 Rationale of SBRT for focal treatment**

Despite the fact that whole gland prostate SBRT is associated low rates of severe grade 3 genitourinary (GU) and gastrointestinal (GI), with adverse effects rates on the order of 1%, lower grade late toxicities are

significantly more common. The most common grade 2 late complications include hematochezia (5-15%), diarrhea (5-10%), hematuria (10-15%), and urethral stricture causing urinary retention (5-10%). Erectile dysfunction will also manifest in more than half of men who are sexually active prior to radiation therapy. By reducing the irradiated volume with focal SBRT, radiation dose to the tissues responsible for the toxicities associated with whole-prostate radiation may be reduced.

One key advantage of SBRT over current focal therapy modalities is the ability to account for microscopic disease extension beyond the imaging abnormality. Whole mount pathology correlate studies have consistently shown that microscopic prostate cancer may extend up to 1 cm beyond the lesion seen on MRI. This discrepancy between imaging and pathologic tumor extension poses a challenge for conventional focal therapies such as HIFU and cryotherapy due to the relatively small area of tumocidal effect around the interstitial probe. In order to account for this limitation, the probe is generally placed in multiple positions in and around the lesion; however, this technique is operator dependent and time consuming. In contrast, SBRT planning techniques allow for the target volume to be enlarged to account for microscopic disease extension (i.e. a clinical target volume expansion) beyond the MRI-defined nodule. Since expansions will generally consist of a geometric margin around the nodule they are less susceptible to inter-operator differences.

Another potential advantage of the SBRT technique proposed in this trial over previously described focal therapy techniques is the ability to administer treatment without violating the perineum. Cryotherapy, HIFU, and photodynamic therapy all require placement of a transperineal interstitial probe. Though the rate of severe complication from probe placement is extremely low, this invasive procedure is uncomfortable and necessitates the use of sedation or anesthesia.

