### **7.6 Adverse event reporting**

- 7.6.1 Notification of all SAE's must be reported to the Principal Investigator ([name]) or his designee by calling [contact]. A written report should be submitted to the appropriate Institutional Review Board (IRB) and UAB Clinical Trials Monitoring Committee per institutional policy.
- 7.6.2 Adverse events will be reported to the Clinical Trials Monitoring Committee.

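### The SAE list in 7.3.2 has no life-threatening, disability or medical-importance criterion, so some grave events outside the urinary and gastrointestinal systems are handled as ordinary AEs

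*Combined protocol and SAP*

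**What the plan says.** Section 7.3.2 defines an SAE as "Any event occurring during the study evaluation period that results in any of the following outcomes". Four outcomes follow: death; "Inpatient hospitalization"; "Bleeding requiring administration of blood products"; and any grade 3 or higher "urinary or gastrointestinal toxicity". The list has no open-ended item and no item that rests on the investigator's judgement.

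The reporting routes depend on this classification:

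- For SAEs, 7.6.1 says "Notification of all SAE's must be reported to the Principal Investigator" or a designee, by telephone. It also asks for a written report to the IRB and the "UAB Clinical Trials Monitoring Committee per institutional policy".
- Section 7.7.2 sends SAEs to a departmental conference and to the quality assurance committees.
- For other events, 7.6.2 says only that "Adverse events will be reported to the Clinical Trials Monitoring Committee".

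Section 7.4.1 applies CTCAE v4.0 grading to adverse events in general. Section 7.7.1 places the study under the cancer center's Data and Safety Monitoring Plan, which is not reproduced.

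**The concern.** Grade decides seriousness in two organ systems only. Elsewhere an event becomes an SAE through death, admission or transfusion, and otherwise not at all, however severe it is. A life-threatening event treated and resolved in an emergency department, or a lasting disability managed in clinic, can therefore rank below a grade 3 urinary symptom. The protocol gives no reason for this ordering.

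What is at stake is escalation. SAE status is what triggers the call to the principal investigator, the IRB report and the departmental review. The protocol contains no study-level stopping rule; 7.8 deals with individual patients only. SAE handling is therefore the main route in the text by which a grave event reaches oversight while the pilot is still running.

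**Working it through.** The plan gives no figure on this point, so the check is mainly one of classification.

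**Step 1. Test events against the four outcomes in 7.3.2.**

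| Event | Death | Admission | Blood products | Grade ≥3 urinary/GI | Outcomes met | Class |
|---|---|---|---|---|---|---|
| Grade 3 urinary toxicity, outpatient | no | no | no | yes | 1 of 4 | SAE |
| Grade 4 GI toxicity, outpatient | no | no | no | yes | 1 of 4 | SAE |
| Bleeding at any site, transfused as outpatient | no | no | yes | no, if outside urinary/GI | at least 1 of 4 | SAE |
| Grade 4 event in another system, admitted | no | yes | no | no | 1 of 4 | SAE |
| Grade 4 event in another system, not admitted or transfused | no | no | no | no | 0 of 4 | AE |
| Persistently disabling event in another system, not admitted or transfused | no | no | no | no | 0 of 4 | AE |

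The gap is the last two rows. No other section adds a seriousness criterion.

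**Step 2. Follow each class through the handling rules.**

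| Requirement in the protocol text | SAE | Ordinary AE |
|---|---|---|
| Recorded in the medical record (7.3) | yes | yes |
| CTCAE grade (7.4.1) and attribution (7.4.2) | yes | yes |
| Followed to resolution or stabilization (7.5) | yes | yes |
| Reported to the monitoring committee (7.6) | yes | yes |
| Counted as toxicity if at least possibly related (11.3.2, 11.3.3) | yes | yes |
| Call to the principal investigator or designee (7.6.1) | yes | no |
| Written IRB report (7.6.1) | yes | no |
| Conference and quality assurance review (7.7.2) | yes | no |

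The two classes differ in the last three rows only. Timing does not separate them in the text: 7.6.1 gives no time limit for SAEs either and leaves the written report to institutional policy.

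**Step 3. Scale.** The documents give no rate for events in the gap, so the rates p below are assumptions. Over the 10 patients in 11.6.1, the chance that at least one man has such an event is 1 − (1 − p)^10, and the expected number of men affected is 10p.

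| Assumed p | Chance of at least one | Expected number of men |
|---|---|---|
| 1% | 1 − 0.99^10 = 9.6% | 0.1 |
| 3% | 1 − 0.97^10 = 26.3% | 0.3 |
| 5% | 1 − 0.95^10 = 40.1% | 0.5 |
| 10% | 1 − 0.90^10 = 65.1% | 1.0 |

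Even at the top of this range, about one man in the study would be affected.

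**The case against.** The strongest reply is that little is lost. Step 2 shows that an uncovered event is still seen, graded, followed and sent to a committee, and 7.8.1 lets the principal investigator withdraw a patient for any clinically significant AE. This stands. A reader might infer that such events go missing, or that a missed event would distort a rate based on 10 men. The documents do not support that: 11.3 counts related AEs and SAEs alike, so no toxicity rate or confidence interval changes.

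A second reply is that the institutional policy in 7.6.1 and the plan in 7.7.1 may already require faster or wider reporting. They are not reproduced, so this cannot be excluded, and the claim is limited to what the protocol text requires. But 7.3.2 states its own definition and does not defer to either document.

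A third reply is that no documented hazard of the technique is shown to fall in the gap. That is also fair. The severe toxicities discussed in 2.5 are genitourinary and gastrointestinal, and 7.3.2 covers those from grade 3. IV contrast (3.3) is discretionary, and the MRI may predate enrollment. A reader might offer erectile dysfunction as a severe disability that the list omits. Section 2.5 says only that "Erectile dysfunction will also manifest in more than half of men who are sexually active prior to radiation therapy". It gives no severity, does not call the effect disabling, and speaks of radiation therapy in general. Sexual function is in any case measured with SHIM and EPIC at the scheduled assessments (Table 8.1, 11.4.2). The point therefore rests on the rule itself and not on a predicted event. Nor do the documents call this the first use of the technique; they describe a pilot feasibility study.

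**Conclusion.** The point holds as a narrow gap in classification and escalation. A non-fatal life-threatening (CTCAE grade 4) or persistently disabling event outside the urinary and gastrointestinal systems, managed without admission or transfusion, meets 0 of the 4 SAE outcomes. Three steps then fall away: the call, the IRB report and the departmental review. Recording, grading, attribution, follow-up and reporting to the monitoring committee remain.

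The number of events is probably small, since many grade 4 events would lead to admission; that is a judgement, as the documents give no rate. The primary endpoint and the descriptive analyses are unaffected. The conclusion assumes that staff classify events by 7.3.2 as written and that the unreproduced institutional documents do not override it. It merits an amendment because it concerns patient safety and is cheap to correct.

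**What to change.** Add three criteria to 7.3.2:

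- any life-threatening (CTCAE grade 4) event, in any organ system;
- any event that causes persistent or significant disability;
- any other event that the investigator judges medically important.

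State that all three follow the routes in 7.6.1 and 7.7.2. Add that expected erectile dysfunction is not by itself a reportable disability unless the investigator judges it so; without that sentence a common effect could generate many reports. If the institutional policy or monitoring plan already uses a wider definition, cite it in 7.3.2 so that the documents agree.

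The cost is a short amendment and a small number of extra reports. Dose, treatment, endpoints, sample size and analysis do not change.

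The same amendment should settle a separate matter in this section: 7.3.1 says that typical urinary or gastrointestinal toxicity up to and including grade 3 is not an AE, while 7.3.2 makes grade 3 an SAE. The two sentences must be reconciled.
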